**Table 1 Threshold Glucose Levels**

| Study Period       | Threshold value          |
|--------------------|--------------------------|
| Baseline to week 8 | >270 mg/dL (15 mmol/L)   |
| Week 8 to week 12  | >240 mg/dL (13.3 mmol/L) |
| Week 12 to week 30 | >200 mg/dL (11.1 mmol/L) |

Values must be recorded on three consecutive days

If the SMBG values are confirmed by central laboratory FPG measurement, then an additional therapeutic intervention should be considered at the discretion of the investigator

*Confidential*

for subjects who are fully compliant with the assigned therapeutic regimen, in the absence of any acute condition that raises blood glucose. Any subject who requires additional glucose-lowering therapy for more than one week should be discontinued (see section 5.2).

## 7 STUDY PROCEDURES

### 7.1 Medical History and Physical Examination

Physical examination will be performed by qualified personnel. A detailed medical history will be obtained at screening (V1).

### 7.2 Height and Weight, CCI [REDACTED]

Height is measured once, at screening.

Body weight CCI [REDACTED] will be measured on fasting (minimum 8 hours) subjects. Duplicate measurements of weight will be performed using digital scales and following emptying of any bowel/bladder contents. Subjects will change into a light hospital gown for weight measurements CCI [REDACTED]. Scales will be calibrated at least monthly using standard weights, and records of calibration will be kept in the study binder. CCI [REDACTED]

[REDACTED] Detailed instructions will be provided in a study manual.

### 7.3 Electrocardiography (ECG)

ECG and vital sign measurements will precede blood draws and study drug administration when scheduled at the same time.

ECGs will be obtained in a quiet environment after remaining in supine rest for at least 5 minutes. Subjects will remain supine but awake during ECG collection. Triplicate ECGs (when required) will be obtained within a 5-minute window and at approximately 1-2 minute intervals. Collection of more ECGs (more replicates) than expected at a particular timepoint is allowed when needed to ensure high quality records.

ECGs may be obtained at additional times when deemed clinically necessary.

ECGs will be digitally recorded and printed on paper. The printed paper ECG will be used for “real time” ECG assessment by the investigator (or designee) who will be responsible for the overall interpretation, determination of the clinical significance and subject eligibility based on the ECG findings. ECG interpretation categories are: Normal ECG, Abnormal ECG – not clinically significant, Abnormal ECG – clinically significant.

The printed ECGs will be retained in the subject’s records at the site. All digital ECG records will also be submitted to the cardiovascular core lab, that will perform the digital ECG analysis and interpretation in this study using standard methodology. If the central

reviewer identifies an abnormality, per the study alert criteria, the investigator will be notified to review the ECG and report any AEs as necessary.

The following variables will be reported: HR, RR, PR, QRS, QT, QTcB, and QTcF intervals.

Any treatment emergent clinically significant ECG finding should be reported as an AE in the eCRF.

#### **7.4 Vital Signs (Blood Pressure and Pulse Rate)**

Vital signs will include only supine blood pressure and pulse rate (after a minimum of 5 minutes rest), and will be assessed following 12-lead ECG (if scheduled) and prior to any blood draws or study drug administration. The values for blood pressure and pulse rate at each time point will be the average of at least three measurements.

#### **7.5 Fasting Self-Monitored Blood Glucose (SMBG) Levels**

Subjects will be provided and trained on use of a glucometer, necessary glucose testing supplies and study diaries at baseline visit (V2), and will be instructed on how to recognize symptoms of hypo- and hyperglycemia. Subjects will be asked to demonstrate competent use of the glucometer at or before their first dosing visit. Results from SMBG will be recorded in the subject diary (section 7.7.2).

All subjects will be instructed to perform fasting SMBG at least three times a week using a portable glucometer. Subjects will record SMBG readings in their diaries. It will be the investigator's responsibility to remind subjects during study visits to perform their routine fasting SMBGs.

Subjects will be requested to perform additional SMBG measurements at any time that they develop symptoms suggestive of hypoglycemia. If subjects experience hypoglycemic symptoms or glucose value  $\leq 70$  mg/dL ( $\leq 3.9$  mmol/L) they should record the SMBG value and symptoms in their diary and take SMBG measurements every 15 minutes until either the symptoms subside or the blood glucose value reaches  $>70$  mg/dL ( $>3.9$  mmol/L).

Subjects who have an out of range SMBG reading (hyperglycemia, see [Table 1](#)) will perform fasting SMBG prior to breakfast on three consecutive days and report the values to the investigator via email or phone if possible on the day each measurement was taken. The investigator will review the results in a timely manner and if possible on the same day as the results were received from the subject.

Subjects who develop/have persistent uncontrolled hyperglycemia or hypoglycemia should contact the clinic. Subjects will be requested to visit the clinic for further testing and appropriate medical management at the investigator's discretion.

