OPK-88003 also produced a dose-dependent weight loss of up to 3.3 kg by week 24. In comparison to placebo and exenatide ER, OPK-88003 50 mg resulted in statistically significant percent change in body weight from baseline at 12 ( $p<0.001$  and  $p=0.011$ , respectively) and 24 ( $p=0.007$  and  $p=0.05$ , respectively) weeks. At least twice as many OPK-88003-50 mg (35.5%) subjects lost  $\geq 5\%$  of their body weight compared to placebo (11.8%) ( $p=0.004$ ) and exenatide ER (18.3%) ( $p=0.025$ ) by week 24.

Safety findings were consistent with what would be expected from a GLP-1 agonist effect. The most frequent OPK-88003 dose-related adverse events (AEs) have been GI symptoms, including nausea, vomiting, diarrhea, and decreased appetite. Most of the events were single episodes, mild in severity, transient and self-limited. These events occurred most commonly after the first dose and the incidence then declined to near control levels by the fourth weekly dose. Rates of nausea, vomiting and diarrhea were dose-dependent with moderate tolerability at the highest dose of 50 mg in study XNAA.

Some injection site reactions (rash/redness) with OPK-88003 treatment were observed although the incidence was lower than for exenatide ER and the severity of the reactions

tended to be mild or moderate with very few severe reactions reported in 3.21% of subjects (9/280). In addition, in almost all cases the reactions decreased in severity over time. Incidence of anti-drug antibodies (ADA) development was <4%.

There was no evidence of a hypoglycemia-promoting effect of OPK-88003. Potential pancreatic AEs occurred in 10 subjects with 11 events requiring adjudication. Of these, only one event in the OPK-88003 treatment group was adjudicated to be an actual pancreatic event.

Mean heart rate (HR) increased with OPK-88003 by approximately 5 beats per minute (bpm) in study XNAA compared to placebo, although the differences were not statistically significant.

Additional safety parameters including SAEs, other treatment emergent adverse events (TEAEs), other laboratory measurements and other vital signs were not different between treatment groups or were modified in a favorable direction by OPK-88003 treatment (notably systolic and diastolic blood pressure).

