26. Have had more than one episode of severe hypoglycemia within 6 months prior to visit 1, as defined by hypoglycemia associated with severe cognitive impairment requiring external assistance for recovery, or has a history of hypoglycemia unawareness or poor recognition of hypoglycemic symptoms. Any subject that the investigator feels will not be able to communicate an understanding of hypoglycemic symptoms and the appropriate treatment of hypoglycemia should also be excluded.

27. Have had two or more emergency room visits or hospitalizations due to poor glucose control within the prior 6 months.
28. Have taken prescription or over-the-counter medications to promote weight loss within the prior 3 months.
29. Have had a significant change in weight, defined as a gain or loss of more than 5% in the prior 3 months.
30. Are currently taking CNS stimulants (eg, Ritalin-SR®) with the exception of caffeinated beverages.
31. Have had a blood transfusion or severe blood loss within the prior 3 months or have known hemoglobinopathy, hemolytic anemia, sickle cell anemia, or have a hemoglobin value <11 g/dL (males) or <10 g/dL (females), or any other condition known to interfere with HbA1c methodology.
32. Blood donation of 450 mL or more in the prior 3 months or any blood donation within the prior month.
33. Have a history of alcohol or drug dependence or abuse within the last 2 years and/or have an average weekly alcohol intake that exceeds 21 units per week (males) and 14 units per week (females) [1 unit = 12 oz. or 360 mL of beer; 5 oz. or 150 mL of wine; 1.5 oz. or 45 mL of distilled spirits].
34. Have a history of atopy (severe or multiple allergic manifestations) or clinically significant multiple or severe drug allergies, or intolerance to topical corticosteroids, or severe post-treatment hypersensitivity reactions (including, but not limited to, erythema multiforme major, linear IgA dermatosis, toxic epidermal necrolysis, anaphylaxis, angioedema, or exfoliative dermatitis).
35. Have a history of acute or chronic pancreatitis or confirmed elevation in serum lipase/amylase (>2 x ULN).
36. Have any other condition or psychiatric disorder that, in the opinion of the investigator, may preclude the subject from following and completing the protocol related procedures.
37. Are unsuitable for inclusion in the study in the opinion of the investigator or sponsor.
38. Are unable to undergo MRI for any reason **CCI**

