**Table 3 Classification of Hypoglycemia**

| Hypoglycemia Level | Glycemic Criteria             | Description  |
|--------------------|-------------------------------|--|
| Level 1            | ≤70 mg/dL (3.9 mmol/L)        | Sufficiently low for treatment with fast-acting carbohydrate and dose adjustment of glucose-lowering therapy |
| Level 2            | <54 mg/dL (3.0 mmol/L)        | Sufficiently low to indicate serious, clinically important hypoglycemia                                      |
| Level 3            | No specific glucose threshold | Hypoglycemia associated with severe cognitive impairment requiring external assistance for recovery          |

[AmDA 4 2018](#)

Subjects should be asked about symptomatic and asymptomatic hypoglycemia at each visit, and trained on treatment of hypoglycemia.

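### Protocol 7.5 lets the 15-minute glucose checks stop on symptom relief alone, so a symptomatic subject may stop while glucose is still at or below 70 mg/dL

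*Protocol*

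**What the plan says.** Protocol section 7.5 starts repeat self-monitoring on either of two triggers: hypoglycemic symptoms, or a glucose value at or below 70 mg/dL (3.9 mmol/L). The subject is then to "take SMBG measurements every 15 minutes until either the symptoms subside or the blood glucose value reaches" more than 70 mg/dL (3.9 mmol/L).

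Table 3, in section 8.3.3, classes a value at or below 70 mg/dL as Level 1 hypoglycemia and describes it as "Sufficiently low for treatment with fast-acting carbohydrate and dose adjustment of glucose-lowering therapy". Below 54 mg/dL is Level 2, described as serious and clinically important.

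The other relevant instructions are these:

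- Routine monitoring (7.5): "All subjects will be instructed to perform fasting SMBG at least three times a week using a portable glucometer".
- New or returning symptoms (7.5): "Subjects will be requested to perform additional SMBG measurements at any time that they develop symptoms suggestive of hypoglycemia".
- Persistent problems (7.5): "Subjects who develop/have persistent uncontrolled hyperglycemia or hypoglycemia should contact the clinic".
- Questions and training (8.3.3): "Subjects should be asked about symptomatic and asymptomatic hypoglycemia at each visit, and trained on treatment of hypoglycemia".
- Exclusion criterion 26 (4.2) removes, among others, anyone who "has a history of hypoglycemia unawareness or poor recognition of hypoglycemic symptoms".

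**The concern.** The two stopping conditions are joined as alternatives, so relief of symptoms is enough on its own. A subject who felt unwell, measured a low value and then felt better may stop testing without any reading that shows recovery. The rule also has no floor: on its literal terms, relief ends the checks even if the last value was in the Level 2 range.

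What is at stake is mainly a small matter of patient safety. There is also a minor data point. Section 8.3.3 asks for the duration of each hypoglycemic event, and SAP 6.11.1 plans listings with glucose values. When checks stop early, the record lacks the value and time at which glucose recovered.

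**Working it through.** The plan states no figure to reproduce on this point. The check has three parts: the logic of the stop rule, the reach of the existing safeguards, and the size of the gap and of the added burden.

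**1. The stop rule in each possible state**, for a subject whose checks have started:

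| Symptoms | Glucose (mg/dL) | 7.5 as written | Stop only above 70 |
|---|---|---|---|
| persist | ≤70 | continue | continue |
| persist | >70 | stop | stop |
| subsided | ≤70 | **stop** | **continue** |
| subsided | >70 | stop | stop |

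Only the third row conflicts with Table 3, and only that row changes under the fix. Two neighbouring cases are not part of the concern. A low value without symptoms is naturally read as needing a value above 70 mg/dL, because there are no symptoms to subside. Symptoms with a value above 70 mg/dL do not meet the Level 1 glucose criterion.

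**2. Whether another instruction covers the third row**

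- Extra testing on symptoms: it depends on symptoms, which have gone in this case.
- Contacting the clinic for persistent hypoglycemia: the subject must know that it persists, and someone who feels well and has stopped testing has no reading to show it.
- Questions at visits: these come later. Visits 10 and 11, for example, are at weeks 16 and 22, six weeks apart.
- Training on treatment: the protocol states no recovery threshold for it.
- Criterion 26: it lowers the risk but requires no reading.

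**3. Size**

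*Time to the next required reading.* Section 7.5 sets a minimum of three fasting readings a week. Spaced evenly over 7 days (an assumption), these leave gaps of 2, 2 and 3 days, with a mean of 7/3 = 2.3 days. After an early stop without returning symptoms, the next reading that 7.5 requires is therefore up to 2–3 days away. Under the fix it is 15 minutes away.

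*Added burden.* Extra fingersticks = minutes at or below 70 mg/dL after symptoms ease ÷ 15. The documents do not give that time, so a range of 15 to 60 minutes is assumed.

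- Routine minimum over treatment: 3 per week × 30 weeks = 90 fingersticks.
- 15 minutes: 15/15 = 1 extra, and 1/90 = 1.1%.
- 60 minutes: 60/15 = 4 extra, and 4/90 = 4.4%.

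*Frequency.* No rate of stopping at or below 70 mg/dL can be derived from the documents. Episodes should be few. Section 1.3 reports that "There was no evidence of a hypoglycemia-promoting effect of OPK-88003", and section 6.9 permits no concomitant glucose-lowering drug other than metformin.

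**The case against.** The strongest reply is that the sentence has two triggers and two matching end-points, and that each end-point belongs to its own trigger. A subject with symptoms and a low reading has met the glucose trigger too, and so would have to reach a value above 70 mg/dL. Likewise, a repeat reading that is still low after symptoms ease would count as a fresh trigger. Both readings are possible, and many sites may apply the rule that way. But the sentence offers the end-points as alternatives and does not say that each is tied to a trigger. A subject whose symptoms ease between two readings could still stop before taking the next one.

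A second reply is that subject-level instructions may already settle the matter. The study manual and the diary instructions were not available for review, so what subjects would be told in practice is unknown. This stands as a limit on the conclusion. However, section 7.5 does not refer to either of them for this rule.

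A third reply is that the contrast between 2–3 days and 15 minutes overstates the harm. It is fair to say that it measures the time to the next required reading and not the time spent in hypoglycemia, and that subjects may test voluntarily or call the clinic sooner. It should be read only in that sense.

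Finally, the safeguards and the low expected frequency make this a minor point. That is accepted. It bears on how much weight the point carries. It is not a reason to leave the wording as it is.

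**Conclusion.** The concern holds as a matter of the protocol's wording. Section 7.5 permits a symptomatic subject to end the checks with glucose still at or below 70 mg/dL, and nothing in the protocol or SAP requires otherwise. The gap is confined to that one state, and the practical weight is small.

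The number of hypoglycemia events, AE severity (graded in section 8.2.1 by interference with activities), Level 3 events, the HbA1c analysis and power are all unaffected. The size estimates rest on two assumptions that the documents do not supply: even spacing of the routine readings, and 15 to 60 minutes at or below 70 mg/dL after symptoms ease. Confidence is medium, because the subject-facing materials could not be checked. The change should be made because it corrects a safety instruction at almost no cost.

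**What to change.** Reword the stop rule in section 7.5 to: *every 15 minutes until the blood glucose value is >70 mg/dL (>3.9 mmol/L), whether or not symptoms have subsided.* Make the same change in the diary instructions if they repeat the rule.

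This also removes any doubt about the low value without symptoms. A subject with symptoms whose reading is already above 70 mg/dL still stops at once, as now. Symptoms that persist or return above that level remain covered by the existing instructions on extra testing and on contacting the clinic. Requiring both conditions before stopping would be stricter, but is not needed to close this gap.

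The cost is a few words of text and one further fingerstick for each additional 15 minutes at or below 70 mg/dL. The SAP, its listings and its analyses need no change.

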## **7.6 Lifestyle Counseling**

At visit 2, subjects will have a lifestyle counseling session (either in a group or individually) with a qualified diabetic educator in accordance with local standards. Subject lifestyle counseling sessions will focus on diet, physical activity and behavioral strategies to achieve a 500-700 kcal/day energy deficit ([AmDA 2018 4](#), [AmDA 2018 7](#)). The sessions will occur approximately every four weeks during the dosing period.

The goals of the counseling session are:

- To promote and support healthful eating patterns, emphasizing a variety of nutrient-dense foods in appropriate portion sizes, to improve overall health
- To address individual nutritional needs based on personal and cultural preferences, health literacy and numeracy, access to healthful foods, willingness and ability to make behavioral changes, and barriers to change
- To maintain the pleasure of eating by providing non-judgmental messages about food choices
- To provide an individual with diabetes the practical tools for developing healthy eating patterns rather than focusing on individual macronutrients, micronutrients, or single foods.

Subjects will be encouraged to increase their physical activity. Activities should progress in intensity, frequency and/or duration to at least 150 minutes per week of moderate-intensity exercise. The subject's average daily level of physical activity will be reviewed as part of the lifestyle counseling.

## **7.7 Diary Completion**

Subjects will complete two separate diaries during study participation. The diaries will be dispensed at visit 2 following randomization, and instructions on diary completion will be provided.

### **7.7.1 Lifestyle Diary**

Subjects should complete a 3-day food intake diary prior to visits 4, 5, 9, 10, 11, 12 and 13, when lifestyle counseling will be provided (see section [7.6](#)). Subjects will also document how much physical activity was performed.

The days recorded in the diary should be in the week prior to the counseling visit and ideally include one weekend day. Information in the lifestyle diaries will be reviewed during the counseling as specified in the schedule of events, and not entered into the EDC.

### **7.7.2 Subject Diary**

Subjects should document date and volume of injection of study drug, results of SMBG, and hypoglycemia and ISRs experienced during the study period.

## **7.8 Clinical Laboratory Tests**

### **7.8.1 Laboratory Parameters**

Clinical laboratory tests to be assessed are indicated in [Table 2](#).

**Table 2 List of Laboratory Tests**

---

|   |  |
|---|--|
| Hematology:  | Serum Chemistry:  |
| 

- Hematocrit (Hct)

- Hemoglobin (Hgb)

- Mean corpuscular hemoglobin concentration (MCHC)

- Mean corpuscular volume (MCV)

- Platelet count

- Red blood cell (RBC) count

- White blood cell (WBC) count with differential

 | 

- Albumin

- Alkaline phosphatase (ALP)

- Alanine aminotransferase (ALT)

- Aspartate aminotransferase (AST)

- Blood urea nitrogen (BUN)

- Calcium

- Creatinine for eGFR

- Creatine kinase (CK)

- Potassium

- Sodium

- Total bilirubin

- Direct bilirubin

- Total protein

- Uric acid

- Lipase

- Amylase

 |
| Urinalysis:  |  |
| 

- Glucose

- Urine leukocyte esterase

- Occult blood

- pH

- Protein

  |  |
| Serology:  | CDC Lipid Panel (fasting):  |
| 

- Hepatitis B surface antigen

- Hepatitis C antibody

  | 

- CDC total cholesterol

- CDC triglycerides

- CDC HDL-C

- CDC LDL-C (calculated)

   |
| Serum calcitonin   |  |
| Hemoglobin A1c (HbA1c)   |  |
| Triglycerides  | Immunogenicity  |
| Glucose (fasting)  | 

- anti-drug antibody (ADA)

- Neutralization assay

  |
| Serum pregnancy test (females)   |  |
| Serum FSH (females)  |  |

CCI

---

### **7.8.2 Immunogenicity**

Blood samples for immunogenicity testing will be collected to determine ADA production. Immunogenicity will be assessed by a validated assay designed to detect ADA in the study drug provided by a specialized laboratory other than the central laboratory. Antibodies may

be further characterized and/or evaluated for their specificity and ability to neutralize the activity of the OPK-88003 at the discretion of the sponsor.

CCI

#### **7.8.4 Sample Collection, Storage, and Shipping**

Collection, processing, storage and shipping procedures will be performed in accordance with the instructions provided by the central laboratory. Detailed instructions will be provided in the laboratory manual. Blood samples will be collected and analyzed for clinical laboratory CCI parameters.

Additional blood draws may be needed for unscheduled visits. Missed samples should be drawn whenever possible. The investigator will provide a temperature monitored space with limited access for the study drug and a -20°C or -70°C freezer space for serum and plasma aliquot storage.

Laboratory samples, including antibody and bioanalytical samples, may be stored according to applicable laws, regulatory requirements or laboratory certification standards.

CCI

